### 3.2 Measures taken to minimize/avoid bias

The subject and parent/legal guardian will be masked to treatment assignment throughout the conduct of the study by use of an “overwrap” label of the marketed product (Proparacaine). A randomization code will be generated by an independent statistician and will assign study drug (AG-920 or Proparacaine) to be received as well as the study eye to be used for each subject.

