### 3.5 Randomization and procedure for breaking the code

A randomization code for allocating the treatments and study eye will be prepared by an independent biostatistician, who is not involved in the day-to-day conduct of the study. Subjects

will be randomized in a 1:1 ratio to receive AG-920 or Proparacaine HCl Ophthalmic Solution. The site will have a randomization list that will assign each subject to treatment and study eye.

The study is single masked. Treatment assignments will be masked to the subjects and their parent/legal guardian only so there is no reason to break the code.

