### 8.3.3 Expedited reporting of Serious and Unexpected Adverse Events

#### Safety reports

An investigator must immediately report to the Sponsor or Sponsor representative any serious adverse event, whether or not considered drug-related, including those listed in the protocol or investigator brochure and must include an assessment of whether there is a reasonable possibility that the drug caused the event. Study endpoints that are serious adverse events (e.g., all-cause mortality) must be reported in accordance with the protocol unless there is evidence suggesting a causal relationship between the drug and the event (e.g., death from anaphylaxis). In that case, the Investigator must immediately report the event to the Sponsor. The investigator must record non-serious adverse events and report them to the Sponsor according to the timetable for reporting specified in the protocol. In case of incomplete information, the Investigator must provide follow-up information as soon as possible, again using the SAE report form.

This requirement applies to occurrences observed during the course of the study and within four (4) weeks of last administration of the study medication.

In addition, in the case of immediately life-threatening AEs or AEs with fatal outcome, or adverse events that are serious, unexpected (i.e., not in the Clinical Investigator’s Brochure) and judged related to the investigational product, the Investigator must inform the Sponsor or Sponsor representative by phone within 24 hours of observation or occurrence of the SAE.

SAEs must be reported to the IRB/EC according to the IRB/EC requirements.

The Investigator/designee will forward all source documents (redacted, if necessary, to maintain the blind) related to the SAE to the Medical Monitor. For each SAE and follow-up to an SAE, the site should ensure that an SAE Narrative and critical baseline CRFs are completed as of the onset date for the SAE (e.g., demographics, concomitant medications, and medical history) and emailed

to [name] (see address below). All SAEs must be reported to [name] via phone or e-mail within 24 hours of becoming aware of the event, whether or not the serious events are deemed drug related. Send to:

[name], FACS

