#### 9.4.2 **Interim analyses**

There is no planned interim analysis.

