### 9.4.5 Protocol Deviations

Important protocol deviations are deviations from the protocol that potentially could have a meaningful impact on study conduct, or on the primary efficacy or key safety outcomes for an individual subject. The criteria for identifying important protocol deviations will be defined within the appropriate protocol-specific document. Important protocol deviations will be reviewed as part of the ongoing data cleaning process and all important deviations will be identified and documented prior to unmasking to confirm exclusion from analysis sets. Further details will be provided in the SAP.

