### 2.4 Randomization

As stated in the protocol, a randomization schedule generated by the Sponsor or designee will be used to assign subjects to each of the two treatment groups with a 1:1 allocation ratio to receive a single dose of AG-920 or Proparacaine according to the randomization schedule.

Study medication will be packaged with an investigational label. Marketed Proparacaine HCl Ophthalmic Solution will be "overwrapped" with an investigational label.

[REDACTED]

[REDACTED]

[REDACTED]

Each eligible subject will be assigned to one of the prepackaged packs available at a site. The study is single masked. Treatment assignments and study medication will be masked to the subjects and their parent/legal guardian only. The treatment randomization number or study medication kit number assigned to the subject will be recorded on the CRF at the site.

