##### Intention-to-treat (ITT) Population

This population is defined as all subjects who are randomized to treatment and have received at least one dose (2 drops) of the study medication. The ITT population is the primary population for efficacy evaluation in this study. Treatment identification is defined in the ITT population by treatment assignment. The ITT population will be identified and finalized before the database is locked and the treatment assignment is merged into the study database.

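### Both documents mask only the family, yet four steps in the plan rely on a sponsor-side blind that no passage sets up

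*Protocol*

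**What the plan says.** **Who is masked.** Protocol 3.2: "The subject and parent/legal guardian will be masked to treatment assignment throughout the conduct of the study". Protocol 3.5 limits masking to those two groups: "Treatment assignments will be masked to the subjects and their parent/legal guardian only so there is no reason to break the code". SAP 2.4 repeats the limit: "Treatment assignments and study medication will be masked to the subjects and their parent/legal guardian only". Protocol 3.5 also says: "The site will have a randomization list that will assign each subject to treatment and study eye".

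**What relies on a wider blind.**
- Protocol 9.3 has PP membership settled by a masked review that precedes unmasking.
- Protocol 9.4.5: "all important deviations will be identified and documented prior to unmasking to confirm exclusion from analysis sets".
- Protocol 8.3.3 has SAE source documents go to the Medical Monitor "redacted, if necessary, to maintain the blind".
- SAP 3.1 has the ITT set finalised "before the database is locked and the treatment assignment is merged into the study database".

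**Related text.** SAP 3.1 has the investigator judge which violations remove a subject from the PP set. Protocol 5.1.2 leaves it to the Sponsor, after medication questions, whether a subject continues and whether later visits enter the safety and efficacy analyses. Protocol 9.4.2: "There is no planned interim analysis".

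**The concern.** If masking stops at the family, the steps that refer to a blind or to unmasking protect nobody in particular. No event counts as unmasking, and no role is told to work without the assignment. A reader of the study report would credit the deviation review and the PP set with a protection that the plan does not provide.

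What is at stake is discretion. Deviation classification, PP membership, adverse event coding, Sponsor decisions on inclusion and late analysis choices could all be made by people who know the arms. The endpoint is one yes/no answer per child in about 60 evaluable children, so moving a single subject can visibly change a comparison.

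**Working it through.** The point is mainly textual, and the plan has no figure of its own to reproduce.

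**Step 1. Set the passages side by side.**

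| Step that presupposes a blind | Who would need to be masked | Is that role masked anywhere? |
|---|---|---|
| PP review (Protocol 9.3) | whoever decides PP membership | No. SAP 3.1 names the investigator, whose site holds the list |
| Important deviations (Protocol 9.4.5) | deviation reviewers | No |
| SAE redaction (Protocol 8.3.3) | Medical Monitor | No |
| ITT set fixed before the merge (SAP 3.1) | data management, statistician | No. The sentence sets timing, not access |

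**Step 2. Could the arm be known before lock?**
- The site has the list (Protocol 3.5).
- The randomization or kit number goes on the CRF (SAP 2.4).
- The monitor verifies kits and comparator bottles (Protocol 3.3.3). The products differ in presentation: a vial against a 15 mL dropper bottle (Protocol 3.3, 6.4.2).
- The code is prepared by an independent biostatistician according to Protocol 3.5, but by the Sponsor or its designee according to SAP 2.4.

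A kit number alone does not give the arm. The gap is that no available passage says who may hold the key linking the two.

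**Step 3. What could one decision do?** Assumed illustration: 30 per arm (the Protocol Summary's approximate figure), 26/30 successes on AG-920 and 30/30 on Proparacaine. One AG-920 failure is then classed as a deviation that removes the child from the PP set.

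Pearson statistic for success/failure counts a, b (AG-920) and c, d (Proparacaine): χ² = N(ad − bc)² / (product of the four margins).
- All children: 60 × (26×0 − 4×30)² / (30×30×56×4) = 864,000 / 201,600 = 4.286, P = 0.038.
- One failure removed: 59 × (26×0 − 3×30)² / (29×30×56×3) = 477,900 / 146,160 = 3.270, P = 0.071.

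The SAP 2.9.1 rule is a 90% CI within ±20% of the reference. I leave out eye side. The reference rate here is 100%, so 20% of it is also 20 points. With s² = Σnp(1 − p)/(N − 2) and SE = √[s²(1/n₁ + 1/n₂)]:
- 26/30: s² = 3.467/58 = 0.0598, SE = 0.0631, lower limit = −13.3 − 1.672 × 6.31 = −23.9 points (fails).
- 26/29: s² = 2.690/57 = 0.0472, SE = 0.0566, lower limit = −10.3 − 1.672 × 5.66 = −19.8 points (passes narrowly).

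The two rules need not move together. Going from 25/30 to 25/28 moves P from 0.020 to 0.066, but the lower limit is −20.3 points and still fails.

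**Step 4. Same decision, ITT.** The ITT set requires randomization and two drops, with no exclusion for deviations (Protocol 9.3, SAP 3.1). The result stays 26/30 v 30/30, P = 0.038. Declaring the outcome invalid does not help AG-920 either, because the first paragraph of SAP 2.8 counts missing or invalid assessments as no effect: again 26/30.

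**The case against.** **The primary analysis is protected.** A reader might infer that one discretionary decision can reverse the primary conclusion. The documents do not support that, for the reason in Step 4. The remaining route to the primary result is the Sponsor's discretion in Protocol 5.1.2, which is worded around later visits after medication questions. Nor is P = 0.05 the sole rule: Protocol 9.4.6 also wants a difference near zero, and SAP 2.9.1 adds the interval criterion. This part of the objection stands and confines the numerical example to the PP analysis.

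**Nobody is said to see results by arm.** A reader might infer that the sponsor and CRO watch success rates accrue, as an informal interim analysis. No passage gives them such results. The merge sentence suggests that the database has no treatment field beforehand, Protocol 3.5 gives preparation of the code to an independent biostatistician, and no efficacy stopping rule exists. Parts of SAP 2.4 are redacted, so handling of packs and codes cannot be fully judged. What stands is narrower: the available text does not prevent it.

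**Single masking is a legitimate design.** Agreed. The site must know what it instils, and this point does not challenge that. But single masking at the site does not require the statistician, coders or deviation reviewers to know the arm, and the plan's own wording assumes that they do not.

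**Conclusion.** The contradiction is in the current text of both documents: masking is confined to the family, while four procedures depend on a blind beyond it. The PP set is the clearest case, since the protocol asks for a masked review and the SAP gives the judgement to the investigator, who is not masked.

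The size is moderate. In the assumed example, one exclusion takes the PP comparison from P = 0.038 to 0.071 and the lower 90% limit from −23.9 to −19.8 points, so an apparent robustness check could cross both thresholds. How often this would happen cannot be derived from the documents. The conclusion that ITT is not exposed in the same way assumes that the first paragraph of SAP 2.8 governs. Its last paragraph treats residual missing data as missing, and Protocol 9.5 carries the last observation forward. The change should be made, but the finding does not show that the primary result is compromised.

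**What to change.** 1. In Protocol 3.2 and 3.5 and SAP 2.4, replace the restriction to the family with wording that also masks, until database lock, the trial statistician, data management and coding staff, and the sponsor and CRO staff who decide deviations and data inclusion. Add the Medical Monitor, unless the assignment is needed for safety.
2. Exempt site dosing staff and the monitor doing drug accountability, who handle visibly different products.
3. Keep the kit-to-arm key with the independent biostatistician and the site, outside the general EDC view. Align SAP 2.4 with Protocol 3.5 on who generates the code.
4. State that no summary by arm is produced before lock.
5. Reconcile SAP 3.1 with Protocol 9.3 so that the masked reviewers, not the investigator, decide PP membership. Without this step, masking the sponsor side leaves the PP route open.

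If the sponsor prefers not to mask these roles, the references to masked evaluation, unmasking and maintaining the blind should be removed.

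The cost is short edits in both documents and minor administrative effort on EDC access. Dosing and safety management at the site are unchanged.

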### **3.6 Participant and Study completion**

#### **3.6.1 Completed subject**

A completed subject is defined as one who completes all Visits (1 and 2) and the Follow Up Phone call.

#### **3.6.2 Non-completing subject/Subject Withdrawal**

A non-completing subject is defined as one who exits the study by their own volition, by decision of their parent/legal guardian, or at the discretion of the Investigator and/or the Medical Monitor. Any subject may decide to voluntarily withdraw from the study at any time without prejudice and the reason will be documented. In the event that discontinuation of treatment is necessary, the Investigator will make every attempt to complete all subsequent safety assessments. Every attempt should be made to keep subjects in the study and to perform the required study procedures, but if this is not possible, the subject may be withdrawn.

All reasonable efforts should be made to contact the subject who is lost to follow-up. These efforts must be documented in the subject's records.

Subjects may be withdrawn from the study for any reason at any time, including but not limited to the following reasons:

- Subject or parent/legal guardian request
- Use of prohibited concomitant medication/therapy
- Lost to follow-up
- Occurrence of AEs that are not compatible with the continuation of the subject in the study, in the Investigator's opinion, or that make it unacceptable to the subject to continue
- Investigator judgment
- Sponsor request

The reason for early discontinuation will be collected.

#### **3.6.3 Discontinuation of the Study**

If the clinical study is prematurely terminated or suspended, the Sponsor or designee will inform the Investigators and the regulatory authorities of the termination/suspension and the reason(s) for the termination/suspension. The Investigators should promptly notify their Independent Ethics Committee (IEC) or Institutional Review Board (IRB) of the termination or suspension and of the reasons.

#### **3.6.4 Discontinuation of a Clinical Site**

The Sponsor reserves the right to close an investigational site or terminate the study in its entirety at any time, for reasonable cause. Reasons for the closure of any investigational site or termination of the study may include:

- Failure to accrue subjects into the study at an acceptable rate.
- Failure of the Investigator to comply with applicable regulations and Good Clinical Practice (GCP) guidelines.
- Submission of knowingly false information from the research facility to the Sponsor, Food and Drug Administration (FDA), or other regulatory authorities.
- Insufficient adherence to protocol requirements and procedures.

If the study is prematurely discontinued, all study data must be returned to the Sponsor or designee. Additionally, the site must conduct final disposition of all unused IMP in accordance with CRO procedures. Study termination and follow-up will be performed in compliance with the conditions set forth in regulatory guidelines.

### 3.6.5 Actions after discontinuation

All subjects who discontinue IMP due to a report of an AE **must** be followed-up and provided appropriate medical care until their signs and symptoms have remitted, stabilized, determined to be chronic, or until abnormal laboratory findings have returned to acceptable or pre-study limits if performed as part of the AE assessment.

For the subject who chooses to withdraw consent or who is non-compliant, every possible effort should be made by the Investigator to perform all examinations listed for Visit 2.

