### 1.2 *Potential Risks and benefits to human subjects*

Minimal risks are expected with AG-920. Based upon clinical trials conducted to date, expected risks for subjects may include temporary, mild conjunctival/ocular hyperemia, eye pain, instillation site reaction (stinging/burning), and conjunctival hemorrhage upon instillation of the investigational medicinal product (IMP). For any additional information on AG-920 use, please refer to the [Investigator's Brochure](#).

Minimal risks are expected with the comparator, Proparacaine HCl ophthalmic solution. Occasional temporary stinging, burning and conjunctival redness may occur with the use of Proparacaine. A rare, severe, immediate-type, apparently hyperallergic corneal reaction (characterized by acute, intense and diffuse epithelial keratitis, a gray, ground glass appearance, sloughing of large areas of necrotic epithelium, corneal filaments and, sometimes, iritis with descemetitis) has been reported. Allergic contact dermatitis from Proparacaine with drying and fissuring of the fingertips has also been reported. For any additional information on Proparacaine use, please refer to the [Package Insert](#).

As this study is to be conducted in healthy pediatric subjects, there is no anticipated benefit other than the possibility that a subject's participation in the present study may help others in the future to have more options for local anesthesia before ophthalmic procedures.

Any new, unexpected adverse events (AEs) present among subjects in this clinical trial will be communicated to Investigators and to ethics committees or Institutional Review Board (IRBs) in accordance with local regulations.

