#### 6.4.3.2 15-60 minutes Post Treatment

Fifteen (15) to 60 minutes after the eye exam, the following examinations will be performed

- Visual Acuity
- External eye exam
- Slit lamp biomicroscopy ONLY if necessary for a suspected AE
- Assess for adverse events and changes in medications
- Schedule Follow-up Phone Call between Days 2-5 (1-4 days following dosing).

*Windows: Times will be measured to the nearest minute*

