### 6.4.4 Follow-Up Phone Call (Day 2-5)

Subjects/parent/legal guardian will receive a phone call from site staff between Days 2-5, which is 1-4 days (24-96 hours post-dose) following treatment with IMP. Subjects/parents/legal guardians will be asked about

- AEs
- Changes to concomitant medications

If there are any ongoing adverse events, the subject will be instructed to return to the investigator's office for appropriate evaluation. If there are no ongoing adverse events, the subject will be considered completed.

Subjects and parents/legal guardians will be thanked for their participation and released to follow their normal standard of care.

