## 8 ASSESSMENT OF SAFETY

### 8.1 Specification of safety parameters

The assessment of safety and tolerability will be evaluated by:

- Visual Acuity
- External eye exam
- Slit lamp biomicroscopy ONLY if necessary for a suspected AE
- AEs (post treatment)
- AEs will be collected at every visit. See Section 8.3 for details on collection and reporting of AEs.

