### ***9.5 Procedure for accounting for missing, unused, or spurious data***

A minimal amount of missing data is expected in this study because of the short duration and the subjects being in the clinic on Day 1. For the ITT population, any missing data on Day 1 will be imputed using the method of last observation carried forward (LOCF), where the closest non-missing value prior to the missing value will be carried forward and imputed for the missing value. The PP and Safety populations will be based on observed data only (without imputation). Any missing, unused, or spurious data will be noted and explained in the final statistical report.

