### ***11.4 Written Informed Consent***

The process of obtaining informed consent must be in accordance with applicable regulatory requirement(s) and must adhere to GCP.

The Investigator is responsible for ensuring that no subject undergoes any study-related examination or activity before the parent(s)/legal guardian(s) have given written informed consent for their child to participate in the study.

The Investigator or designated personnel will inform the parent(s)/legal guardian(s) of the objectives, methods, anticipated benefits and potential risks and inconveniences of the study. The parent(s)/legal guardian(s) should be given every opportunity to ask for clarification of any points s/he does not understand and, if necessary, ask for more information. At the end of the interview, the parent(s)/legal guardian(s) will be given ample time to consider the study. The parent(s)/legal guardian(s) will be required to sign and date the ICF. After signatures are obtained, the ICF will be kept and archived by the Investigator in the Investigator's study file. A signed and dated copy of the subject ICF will be provided to the subject's authorized representative.

It should be emphasized that the parent(s)/legal guardian(s) may refuse permission for their child to enter the study or may withdraw their child from the study at any time, without consequences for their further care or penalty or loss of benefits to which the subject is otherwise entitled. Children of parents(s)/legal guardian(s) who refuse to give or who withdraw written informed consent should not be included or continue in the study.

If new information becomes available that may be relevant to the willingness of the subject's parent(s)/legal guardian(s) to allow continuation of their child's participation in the study, a new ICF will be approved by the IEC(s)/IRB(s) (and regulatory authorities, if required). The parent(s)/legal guardian(s) of the study subjects will be informed about this new information and reconsent will be obtained.

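### A missing primary answer has conflicting rules, one of which (LOCF) cannot produce a value; as a minor separate matter, protocol 3.6.5 clashes with 11.4 once consent is withdrawn

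*Protocol*

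**What the plan says.** **Missing primary answer.** Protocol 9.5 says that for the ITT population "any missing data on Day 1 will be imputed using the method of last observation carried forward (LOCF"), using the closest earlier non-missing value. In SAP section 7, the titles of Tables 2.1.1 (ITT primary analysis) and 2.1.3 (by-site summary) carry the LOCF label. SAP 2.9.1 refers missing values to SAP 2.8. The first paragraph of SAP 2.8 counts an answer missing through invalid data or early termination as no anesthetic effect. Its last sentence says that resultant missing efficacy or safety data are treated as missing. The per-protocol rule, observed data only, is the same in both documents.

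**Consent.** Protocol 3.6.5 says that for a child "who chooses to withdraw consent or who is non-compliant, every possible effort should be made by the Investigator to perform all examinations" of Visit 2. Protocol 11.4 says that children of parents "who refuse to give or who withdraw written informed consent should not be included or continue in the study". Protocol 3.6.2 uses similar effort wording but then gives way: "but if this is not possible, the subject may be withdrawn".

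**The concern.** The primary ITT table needs one stated rule. LOCF presupposes an earlier value of the same measurement. Protocol Table 1 schedules the eye exam procedure once, 2-4 minutes after the last drop, and SAP 2.6 has the investigator asked once, after treatment. LOCF therefore returns nothing, and in practice the child drops out of the calculation. SAP 2.8 instead keeps the child as a failure. With about 30 to 35 children per arm, one answer moves a proportion by 2.9 to 3.3 points, and both equivalence rules in SAP 2.9.1 (P > 0.05, and the 90% CI within ±20%) depend on those proportions.

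On consent, protocol 3.6.5 treats withdrawal of permission like non-compliance, where permission still stands. It names no condition of parental agreement and no stopping point. Protocol 1.2 states: "As this study is to be conducted in healthy pediatric subjects, there is no anticipated benefit", apart from possibly helping others. In that population, what a site may do after permission ends should be explicit.

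**Working it through.** **1. The rules side by side, for an ITT child with no answer**

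| Source | Rule | Result |
|---|---|---|
| Protocol 9.5; titles of SAP Tables 2.1.1 and 2.1.3 | LOCF | No value: no earlier assessment exists |
| SAP 2.8, first paragraph (via SAP 2.9.1) | Score NO | Child stays in the denominator as a failure |
| SAP 2.8, last sentence, read literally | Treat as missing | Child leaves the denominator |

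The working choice is thus scored NO or left out.

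**2. Does the choice matter?** The documents give no response rates or missing counts, so the counts below are assumptions. Arm sizes of 35 and 30 follow from 70 enrolled and 60 evaluable at 1:1. One child is 1/35 = 2.9 points or 1/30 = 3.3 points.

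The 90% CI follows the SAP 2.9.1 linear model with eye side balanced. With d = p1 - p0, the interval is d ± t(0.95, N-3) × √[s²(1/n1 + 1/n0)], where s² = [n1·p1(1-p1) + n0·p0(1-p0)]/(N-3).

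Worked case: 35 per arm, proparacaine 35/35 YES, AG-920 with three observed NO and one missing.

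- Scored NO, 31/35: d = -11.43; s² = 3.543/67 = 0.0529; SE = 5.50; t = 1.668; limits -20.6 to -2.3. Outside.
- Left out, 31/34: d = -8.82; s² = 2.735/66 = 0.0414; SE = 4.90; t = 1.668; limits -17.0 to -0.6. Inside.

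The Pearson statistic (protocol 9.4.6) is d²/[p̄(1-p̄)(1/n1 + 1/n0)]. Scored NO, p̄ = 66/70: χ² = 4.24, P = 0.039. Left out, p̄ = 66/69: χ² = 3.23, P = 0.072. The CMH test (SAP 2.9.1), ignoring eye-side imbalance, multiplies χ² by (N-1)/N and gives P of about 0.041 and 0.074. The P > 0.05 rule changes as well.

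Lower 90% limits for other assumed counts, each with one missing AG-920 answer:

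| Per arm | Proparacaine NO | AG-920 observed NO | Scored NO | Left out | ±20 verdict |
|---|---|---|---|---|---|
| 35 | 0 | 2 | -16.6 | -12.7 | Same (inside) |
| 35 | 0 | 3 | -20.6 | -17.0 | Changes |
| 35 | 0 | 4 | -24.4 | -21.1 | Same (outside) |
| 35 | 1 | 4 | -22.6 | -19.4 | Changes |
| 30 | 0 | 2 | -19.4 | -14.8 | Same (inside) |
| 30 | 0 | 3 | -24.0 | -19.9 | Changes |
| 30 | 0 | 4 | -28.3 | -24.6 | Same (outside) |

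With proparacaine all YES and zero or one observed AG-920 NO, both rules are inside at both sizes. With a 100% reference rate, ±20 points and 20% of the reference coincide. In the row with one proparacaine NO, 20% of the reference is 0.20 × 34/35 = 19.43 points, and the left-out limit of -19.40 is still just inside. In that row Pearson P is 0.088 (χ² = 2.92) or 0.154 (χ² = 2.04), so only the ±20% rule changes.

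**3. The consent wording**

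Protocol 3.6.5 covers every Visit 2 examination. That includes the 2-4 minute eye exam that yields the primary answer (protocol 6.4.3.1) and the later checks: "Fifteen (15) to 60 minutes after the eye exam, the following examinations will be performed", chiefly visual acuity and external eye exam. Protocol 8.1 counts these two as safety measures: "The assessment of safety and tolerability will be evaluated by" them, among others. The later checks fall 2 + 15 = 17 to 4 + 60 = 64 minutes after the last drop. Each affected family is 1 of up to 70, or 1.4%; the number is not given.

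A child withdrawn between the second drop and the eye exam has had both drops, so is in the ITT population without an answer. The two parts of this point meet there.

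**The case against.** On missing data, the documents can be read to one answer. Protocol 9.4.1 leaves fuller methods to the SAP, SAP 2.9.1 points to SAP 2.8, and SAP 2.8 says NO. *Resultant* in its last sentence most naturally means whatever is left after that rule, and the LOCF titles look like leftover labels. Table 1.6.1 reports missing data and imputation, Listing 6 shows answers with and without imputation, and the per-protocol analysis uses observed data, so a reader could see any effect. ITT requires both drops, the question follows within minutes, and protocol 9.5 expects minimal missing data. All of this limits the damage. It does not remove the mismatch: the protocol names a rule that cannot work, and the SAP's own primary table carries its label.

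On consent, protocol 11.4 lets parents withdraw at any time without consequences and says the child should not continue. Protocol 3.6.5 asks for effort and does not authorize examination over a refusal. A site can satisfy both sections by asking and stopping if refused. The consent form is not among the pages available, so its wording cannot be judged. The later checks also serve a child who has just been dosed. That reduces this part to a minor clarification.

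That 3.6.5 omits the Day 2-5 call is not a defect. Protocol 6.4.4 provides that "Subjects/parent/legal guardian will receive a phone call from site staff between Days 2-5", and SAP 2.2 applies the call to all randomized, dosed subjects.

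**Conclusion.** The missing-answer rule is wrong as written and should be corrected: LOCF cannot produce a value and conflicts with SAP 2.8 for the primary ITT analysis. Its effect is confined to the edge. One missing AG-920 answer can move the 90% lower limit from -17.0 to -20.6 points and P from about 0.074 to 0.041 in the worked case. This rests on assumed counts, balanced eye sides and few missing answers.

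The consent wording is a minor clash with a cheap correction.

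Three stronger readings are tempting, and the documents do not support them:

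- That the protocol leaves families unprotected after withdrawal, or permits examination over a refusal. Section 11.4 says otherwise.
- That the consent wording cannot touch the primary result. The 2-4 minute eye exam is itself a Visit 2 procedure.
- That the primary analysis has no usable rule. SAP 2.9.1 leads to the NO rule, and the listings show the imputation.

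Nor should the table be taken to mean that only three AG-920 NO answers matter. Other assumed counts change the verdict too.

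**What to change.** **Missing primary answer.** Keep the NO rule of SAP 2.8 for the ITT primary analysis. Remove LOCF for this endpoint from protocol 9.5 and from the titles of SAP Tables 2.1.1 and 2.1.3. Limit the last sentence of SAP 2.8 to safety parameters and the observed-data per-protocol analysis. Cost: one sentence in each document and two table titles.

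**Consent.** In protocol 3.6.5, limit the effort sentence to non-compliant subjects whose permission still stands. Add that after permission is withdrawn, only procedures the parent specifically agrees to are done, such as the remaining post-dose safety checks or the Day 2-5 call, and that the agreement is documented. Medical follow-up of adverse events in the first paragraph of 3.6.5 is unchanged. Cost: one reworded sentence and a short addition. The downside is slightly less post-dose data from families who decline, and a child withdrawn between the second drop and the eye exam would be scored NO in the ITT analysis.
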